[name] Research Bio. Med. Lab. Technologist SDCN Aalborg University

[name] [name]. SDCN Aalborg University Hospital

II. BACKGROUND AND SIGNIFICANCE

A. Background

Diabetes Mellitus (DM) is a growing healthcare problem worldwide[1] and currently affects more than 451 million people[2]. DM is associated with excess morbidity and mortality[3][4] with diabetic peripheral neuropathy (DPN) being the most common of the classic diabetic complications[5]. This means, that half the diabetic population will develop DPN during their lifetime[6]. Moreover, DPN is also the leading cause for disability in diabetic patients, mainly due to its complications including autonomic disturbances and events related to the diabetic foot. The most important being diabetic foot ulcers, foot amputations, and the Charcot neuroarthropathy (CN), while approximately 20-30% of patients will suffer from invalidating neuropathic pain at some point during their lifetime[7]. Furthermore, diabetic foot ulcers have been associated with ischemic heart disease (IHD), which is the leading cause of premature mortality in patients with DM[8]. At the same time, the five-year mortality after new-onset diabetic ulceration have been reported to be 43-55%, and 74 % in patients with diabetic foot amputation, which is significantly higher than the five-year mortalities for many forms of cancer[9].

Despite this, our knowledge is quite limited when it comes to risk stratification of the diabetic patients. It is clear that DPN is the single most important risk factor for development of complications regarding the diabetic foot whether talking about foot ulcers[10], amputations[11], or CN[12]. However, the current clinical tests to detect DPN are unspecific and with questionable sensitivity reported as low as 0.53[13]. Furthermore, the current clinical tests are solely assessing large fiber neuropathy and are not able to do a meaningful grading of the severity of the neuropathy, hence the need for new methods to provide efficient clinical outcome measures and useful clinical endpoints.

B. State-of-the-Art

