
III. STUDY OBJECTIVES

To test Perception Threshold Tracking (PTT) and multi-level MRI as methods for early detection and grading of severity of neuropathy in patients with diabetes mellitus.

To use multi-level MRI for characterization of peripheral and central nervous system changes related to neuropathy in patients with diabetes mellitus.

To compare Perception Threshold Tracking (PTT) and MRI to methods of traditional clinical practice and established methods of clinical research like Corneal Confocal Microscopy (CCM) and Quantitative Sensory Testing (QST) as well as axon flair-mediated neurogenic vasodilation (AF).

To test reliability of different measurements of neuropathy.

A better understanding of the underlying neuropathy of diabetes and new methods for early, reliable detection of DPN could result in intensified treatment and prophylactic measures prolonging of the complicationfree period of diabetes mellitus. Ultimately, this could potentially result in fewer complications related to the diabetic foot, and maybe even prolonged overall-survival and reduced healthcare cost.

IV. METHODS

A. Study Design

This study is a prospective, observational, cross-sector study starting March 1, 2019 running until December 1, 2021. The study will be conducted on patients from Aalborg University Hospital. Participants will be informed about the trial both written and vocally and no changed in antidiabetic medication will be performed. The instruments will include Corneal Confocal Microscopy (CCM), Quantitative Sensory Testing (QST), axon flair-mediated neurogenic vasodilation (AF), handheld heart rate measurement device (Vagus[™]), cuff, and MRI, which are all established methods of clinical research. Furthermore, participants will be tested using monofilament and Biothesiometry, which equals actual clinical practice, and with Perception Threshold Tracking (PTT), which is a new take on an older, well-known technology. Further tests will include a handheld pinprick device, measurements of peripheral arterial disease (PAD) and conventional NCS. The main endpoint of the study will be sensitivity/specificity of all examinations, as well as a comparison of the newer methods against more well-established modalities.

B. Study Population

The study population include four well-defined groups of subjects:

- 1. Patients with Type 1 diabetes and painful diabetic peripheral neuropathy (DPN).

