- 2. Patients with Type 1 diabetes and non-painful diabetic peripheral neuropathy (DPN)
- 3. Patients with Type 1 diabetes and without diabetic peripheral neuropathy (DPN).
- 4. Healthy control subjects matched for age, BMI, and gender.

Diabetes duration, HbA1c, insulin use, ethnicity, and co-morbidities will be matched between group 1, 2 and 3 to best ability.

Inclusion criteria:

- 1. Men and women minimum 18 years of age and maximum 70 years of age
- 2. Signed informed consent form
- 3. Diagnosed with diabetes type I (for group 1-3)
- 4. Diagnosed with DPN defined as a threshold above 25-volt biothesiometry or absent feeling on the big toe using 10g-monofilament. (for group 1-2)
- 5. Answered questionnaire: PainDETECT
- 6. Nothing abnormal on initial tests (group 4)
- 7. Accepted initial screening blood samples
- 8. MRI-compatible participant

Exclusion criteria:

1. Current or previous alcohol- or drug abuse

- 2. Abnormal screening blood samples
- 3. Not being able to understand Danish written and/or verbally
- 4. Not being able to corporate to examination (e.g. not being able to speak, suffering from senile dementia etc.)
- 5. Previous chemotherapy or intake of experimental medicine
- 6. Active HSV- or VZV-infection or known HIV
- 7. Known severe skin disease
- 8. Known neural damage or disease in the neural system (e.g. MS, Guillain-Barre etc.)
- 9. Critical limb ischemia defined as in current clinical consensus[63]
- 10. Allergy or intolerance to histamine or inability to make do without for one day
- 11. Pregnancy
- 12. Active cancer-disease

C. Assessment of Resources

The study will be conducted in collaboration with Steno Diabetes Center Northern Denmark (SDCN) and Department of Radiology, Aalborg University Hospital. SDCN has access to patients with diabetes and can provide the necessary premises.

The study will be conducted in collaboration with Center for Neuroplasticity and Pain (CNAP), Aalborg University and SDCN, who have the technical and financial resources needed to establish the setup and conduct the examinations. Furthermore, an experienced research Bio. Med. Lab. Technologist is signed for the project thereby, alongside the Ph.D.-students, ensuring trained personnel. The study is set for a long inclusion, but additional time is available if required, as the Ph.D.-students are employed until 31st of October 2022.

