The project is initiated by [name], Aalborg University and SDCN, and is supported economically by Steno Diabetes Center North Denmark and Aalborg University. The support is however limited to staff salary and purchase of smaller equipment.

D. Study Procedures

Diabetic patients will be recruited during their scheduled visit to the outpatient clinic of SDCN, Aalborg University Hospital. Healthy controls will be recruited based on the included diabetic population using relatives of diabetic patients, medical students, and people known by participating staff.

After the informed consent is obtained the screening of the participant will be executed. Afterwards the participant have to attend three different sessions as shown in appended flowchart. Each session includes different tests and the sessions will be ordered randomly, since they have no influence on each other. Moreover, a conventional nerve conduction test will be performed, however this test will be performed as per usual by the department of neurophysiology, as this is a standard examination for patients with neuropathy.

PainDETECT

PainDETECT is an English questionnaire validated for detecting neuropathic pain[64]. It has later been translated and validated in Danish[65], and will be given each participant alongside instructions after form of consent has been signed. The patients will answer the questionnaire individually and will need to complete this before any other examinations can be conducted, as this will help placing the patients in the correct group.

Estimated time: 5-15 min.

Clinical examination

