To avoid 'mass significance' a combined analysis of all measurements will be performed by logistic regression models (LRM) in three steps. This will allow an estimate of the odds ratio and accuracy of each of the measurements and the measurements in combination. First, a series of univariate LRM will be performed for each measurement to investigate the odds ratio and accuracy of the individual. Second, a multiple factor LRM with all measurements as factors will be performed to estimate the odds ratio and accuracy for all measures in combination. Thirdly, factor reduction will be performed to assess the accuracy and odds ratio of a set of independent measures.

Simple bivariate correlation will be performed to further investigate the relation between measurements. Due to the complexity of the measurements a further analysis of the interdependency of the measures using factor analysis will be performed.

VII. DATA AND SAFETY MONITORING PLAN

The project will be reported to the Data protection Agency (DPA), and all sensitive data will be stored in either Red-CAP or on the protected server of Aalborg University Hospital, *"Elektronisk system adgang"* (ESA).

Data are stored in accordance with the stipulations in The Danish Personal Data Protection Act (Persondataloven) and other relevant Danish legislation. If any data processing would occur in foreign countries, the data will be anonymized and handled according to the Danish Data Protection Act.

The data can only be used for the interpretation of this project and will therefore not be of interest to third party.

The project is included in "Region Nordjyllands fællesfortegnelse".

VIII. STUDY LIMITATIONS

Both PTT and QST require corporation from the patients and include subjective measures of pain. As the measured thresholds are not purely objective, psychosocial factors might influence test results.

The study includes diabetic patients exclusively and might not be applicable on populations with different causes of neuropathy.

The expected number of participants are set at 80, thus maybe require additional larger studies to confirm findings.

IX. ETHICAL CONSIDERATIONS

A. Informed Consent

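### VI.B plans no paired comparison of accuracy between methods, and the apparent reference is defined by two of the tests to be scored

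*Combined protocol and SAP*

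**What the plan says.** IV.A (Study Design) sets the main endpoint as "sensitivity/specificity of all examinations, as well as a comparison of the newer methods against more well-established modalities". It lists biothesiometry and monofilament among the tests every participant receives. The third objective in section III is "To compare Perception Threshold Tracking (PTT) and MRI to methods of traditional clinical practice and established methods of clinical research", with corneal confocal microscopy (CCM), quantitative sensory testing (QST) and the axon flare test (AF) as the research comparators.

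IV.B (Study Population) gives the only definition of DPN, for groups 1 and 2: "Diagnosed with DPN defined as a threshold above 25-volt biothesiometry or absent feeling on the big toe using 10g-monofilament". Group 3 is described as type 1 diabetes without DPN and has no definition of its own.

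VI.B starts with ANOVAs across the four groups. Logistic models follow in three steps, of which it says: "This will allow an estimate of the odds ratio and accuracy of each of the measurements and the measurements in combination". In the second step, "a multiple factor LRM with all measurements as factors will be performed". Bivariate correlation and factor analysis complete the plan. The dependent variable of the logistic models is not stated, accuracy is not defined, and no confidence interval is mentioned.

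**The concern.** The endpoint asks which method discriminates better. The planned analyses answer other questions. ANOVA shows whether group means differ. An odds ratio depends on the scale of its measure and cannot be ranked across methods. Correlation shows whether two methods move together. A reader would be left with per-method accuracies side by side and no interval on the gap, so a chance difference between PTT or MRI and an established method could be taken as real.

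There is also a circularity. If DPN group is the reference, two of the examinations are judged against a label they created. That fixes part of their accuracy in advance, tilts any comparison with them, and undermines the joint model.

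Finally, the label is a large-fibre one. II.A says that "the current clinical tests are solely assessing large fiber neuropathy", while the study's aim is early detection. A method that correctly picks up small-fibre damage in group 3 would be counted as giving false positives.

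**Working it through.** **1. What the plan's own numbers cover.** VI.A: n = 15.7 × (4.7² + 7.5²) / (14.4 − 5.7)² = 15.7 × 78.34 / 75.69 = 16.25, taken as 16. Then 16 / 0.8 = 20 per group, and 4 × 20 = 80. The stated figures reproduce. They concern a difference in mean nerve-conduction amplitude and say nothing about the precision of an accuracy comparison.

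**2. Which reference.** VI.B does not say. Three things point to DPN group: criterion 4 is the only DPN definition, VI.A sizes the study on separating patients with and without neuropathy, and the ANOVAs compare the groups. The contrast is then groups 1+2 (40 people) against group 3 (20 people).

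**3. Circularity on that reading.** Let V be the biothesiometry reading in volts and M = 1 if big-toe feeling is absent. A case has V > 25 or M = 1. If group 3 is everyone who does not meet the criterion, a non-case has V ≤ 25 and M = 0.
- Each test at its entry limit: no group 3 patient is positive, so specificity is 100%.
- The two together (either positive): sensitivity is 100% and specificity is 100%.
- Each test alone: sensitivity is not fixed. Every case is positive on at least one test, so the two sensitivities need only sum to at least 100%.

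**4. Separation in the joint model.** Take the score b1(V − 25) + b2·M with b1 > 0 and b2 > 25·b1.
- Case with M = 1: since V ≥ 0, the score is at least b2 − 25·b1 > 0.
- Case with M = 0: V > 25, so the score is above 0.
- Non-case: the score is at most 0.

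The groups are separated, and maximum likelihood gives no finite odds ratios. This needs no simulation, but it does require that the entry readings are the ones modelled.

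**5. Precision of a paired AUC difference.** The documents give no AUCs or correlations, so these are assumed: binormal data with equal SDs, AUC 0.90 against 0.80, and within-group correlation r between the two methods. Evaluable numbers are 40:20 as recruited, or 40 × 0.8 = 32 and 20 × 0.8 = 16 if the same 20% lack both measures. The 95% half-width is 1.96 × the mean paired DeLong standard error:

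| Evaluable | r 0 | r 0.5 | r 0.7 | r 0.8 |
|---|---|---|---|---|
| 40:20 | 0.14 | 0.11 | 0.09 | 0.08 |
| 32:16 | 0.16 | 0.13 | 0.11 | 0.09 |

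**6. Precision of paired sensitivity and specificity.** The half-width is 1.96 × √(discordance / n) when the true difference is 0. Discordance of 0.2 to 0.4 is assumed.
- Sensitivity, n = 40: 1.96 × √(0.2/40) = 0.139 to 1.96 × √(0.4/40) = 0.196.
- Specificity, n = 20: 0.196 to 0.277.

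**7. Does dropping the two defining tests cure separation?** QST gives 13 parameters and the MRI session lists six components. With one value each for PTT, nerve conduction, CCM, AF and the handheld autonomic test, that is 13 + 6 + 5 = 24 factors, if each MRI component yields one value. In simulated 40:20 samples (assumed AUC 0.70 per measure, pairwise r 0.3, defining tests excluded), the groups still separated in about 41% of samples with 20 measures and 98% with 30. With six measures, separation occurred in none of 400 samples.

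**The case against.** The strongest reply is that the circularity is inferred. VI.B never states the outcome, and nerve conduction could be meant as the reference, since IV.D presents it as the standard for large-fibre function. This stands as a limit. But an unstated reference for an accuracy endpoint is itself a gap, and with nerve conduction as reference the circularity would move to nerve conduction, which is also one of the examinations.

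IV.D applies the monofilament at four spots, while the entry criterion uses the big toe. The modelled result may therefore differ from the entry result, which would soften the circularity.

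Three stronger readings are tempting, and the documents do not support them:
- A reader might infer that biothesiometry and monofilament would each look close to perfect. Under an either-or rule only the specificity of each is fixed; neither alone is guaranteed high sensitivity.
- A reader might infer that a 0.10 gap can never be told from chance in this study. With r of 0.7 to 0.8 and 40:20, the half-width falls below 0.10, and tests of one disease in the same people could correlate that strongly.
- A reader might infer that small-fibre methods are certain to be under-rated. II.B says most studies find early damage mainly in small fibres, but it also reports mixed results. The size of any bias is unknown.

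**Conclusion.** The point holds. The main endpoint calls for a comparison of accuracy between methods, and VI.B plans no estimate or interval for it; that follows from the text alone. The reference and logistic outcome are unnamed. If they are DPN group, and group 3 is the complement of the entry criterion, the two defining tests have 100% specificity by construction, jointly have 100% sensitivity, and separate the groups in the joint model.

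Under the assumed AUCs, the half-width of a paired AUC difference is 0.08 to 0.16 across r 0 to 0.8 and both evaluable sizes. A gap of 0.10 is often, but not always, within noise, which is why an interval matters. The large-fibre reference may also disadvantage small-fibre methods, by an amount the documents do not let one estimate. This should be corrected in the analysis plan; it does not call for a different study.

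**What to change.** Amend VI.B as follows.

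1. Name the reference and the logistic outcome: groups 1+2 against group 3. Keep healthy controls out of specificity; they must be normal on the initial tests and are drawn from "relatives of diabetic patients, medical students, and people known by participating staff".
2. Pre-name one summary measure each for PTT, MRI, nerve conduction, CCM, QST and AF. For QST, choose one other than its vibration or touch threshold, which resemble the defining tests. State the role of MRI, because IV.A lists it as established while the third objective puts it under test.
3. Report paired differences with 95% confidence intervals for PTT and MRI against each comparator: sensitivity and specificity at pre-stated cut-offs, which is the protocol's own endpoint, and/or AUC by DeLong's method. Say that a non-significant difference is not equivalence.
4. Do not score biothesiometry or monofilament against group membership, and leave them out of the logistic models for that outcome. State that the comparison with current clinical practice needs another reference, and that nerve conduction is offered for large-fibre function only.
5. Limit the joint model to the pre-named measures, or use a penalised fit such as Firth's. Step 4 alone does not prevent separation.
6. State the large-fibre reference as a limitation.

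The cost is wording and standard analyses on data already planned, with no extra participants. The intervals will be wide. The reference bias is disclosed but not removed, and the comparison with current clinical tests stays open until another reference is named.

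### The two tests that define DPN are also scored for accuracy and entered in the regression models; if the groups are the reference, part of their result is fixed in advance.

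*Combined protocol and SAP*

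**What the plan says.** The label is set in section IV.B, criterion 4, for groups 1-2: "Diagnosed with DPN defined as a threshold above 25-volt biothesiometry or absent feeling on the big toe using 10g-monofilament". Group 3 is type 1 diabetes without DPN and has no rule of its own. Group 4 must have normal initial tests, which are not named.

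Section IV.A lists the same two tests as study examinations: "participants will be tested using monofilament and Biothesiometry, which equals actual clinical practice". It then states: "The main endpoint of the study will be sensitivity/specificity of all examinations". Section III adds a comparative aim: "To compare Perception Threshold Tracking (PTT) and MRI to methods of traditional clinical practice".

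Section VI.B plans three LRM steps: "First, a series of univariate LRM will be performed for each measurement", then "a multiple factor LRM with all measurements as factors will be performed", then "Thirdly, factor reduction will be performed to assess the accuracy and odds ratio of a set of independent measures". It also plans analyses that do not use the label: "Simple bivariate correlation will be performed to further investigate the relation between measurements", and a factor analysis.

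No section excludes biothesiometry or monofilament from any of this, names the reference for sensitivity and specificity, or names the LRM outcome. Under Clinical examination, section IV.D says that the filament is applied at four spots, that results may be combined into a Neuropathy Disability Score (NDS), and that these examinations may also take place at a later session. It describes nerve conduction (NCS) as the gold standard, but for large fibres only.

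**The concern.** A test that helps to define the disease label cannot be given a fair accuracy estimate against that label (incorporation bias). Here the rule is an either/or. Anyone without the label is therefore negative on both tests, and anyone with it is positive on at least one.

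This touches the main endpoint and the third objective. If PTT or MRI is set beside clinical practice on specificity in group 3, the clinical tests start from a perfect score that reflects selection. A group 3 patient with early neuropathy that the label misses counts as a false positive for the newer test, although early detection is the first objective and section II.A itself calls the current tests insensitive. In the LRMs, a factor reduction guided by fit or in-sample accuracy can stop at the two defining tests, report 100% accuracy, and leave the impression that the newer measures add nothing.

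**Working it through.** **Inputs.** From IV.B: the either/or rule, and group 3 read as its complement. From VI.A: the group sizes. The plan gives no accuracy figure to reproduce. Its sample size does reproduce: 15.7 × (4.7² + 7.5²) / (14.4 − 5.7)² = 15.7 × 78.34 / 75.69 = 16.25, stated as 16; 16 / 0.8 = 20 per group; 4 × 20 = 80. Groups 1-2 therefore hold 40 and group 3 holds 20, or 32 and 16 at the planned maximum dropout.

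**Accuracy table.** Let V be the volts, M = 1 if the big toe is not felt, and D = 1 if V > 25 or M = 1.

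- Group 3 has D = 0, so V ≤ 25 and M = 0 for everyone. Specificity of each test is 20/20 (or 16/16) = 100%.
- Groups 1-2 have D = 1, so everyone is positive on at least one test. Sensitivity of the either-positive rule is 40/40 (or 32/32) = 100%.
- Each test's own sensitivity is not fixed. The two positive counts need only sum to at least 40, so the two sensitivities sum to at least 100%. On sensitivity a newer test can still beat either test alone.
- Each group 3 patient flagged by a newer test costs it 1/20 = 5 percentage points of specificity. Its best result is a tie.

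**Models with D as outcome.** Take S = V + K·M with K > 25.

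- D = 0: S = V ≤ 25.
- D = 1 with M = 1: S ≥ K > 25.
- D = 1 with M = 0: S = V > 25.

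So S exceeds 25 exactly when D = 1, which is complete separation. With K = 26 and a cut at 25.25, none of the 202 combinations of V = 0 to 50 in steps of 0.5 (assumed range) and M = 0 or 1 is misclassified. Finite maximum-likelihood odds ratios do not exist, and further factors cannot undo this. A dichotomised defining test alone has a zero cell: with a > 0 positives in groups 1-2, the odds ratio is (a × 20) / ((40 − a) × 0), which is infinite. Continuous biothesiometry alone need not be separated.

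**How much of the full LRM's trouble is due to these tests.** A minimum count of the other measures in IV.D is QST 13 + MRI 6 + Vagus 4 + PTT 2 + CCM, AF, NCS and pinprick 1 each = 29 factors, for 60 participants in groups 1-3. In linear-programming checks with 29 simulated normal factors and neither defining test, 40 versus 20 was separated in roughly two-thirds of sets with pure noise. With an assumed 0.3 SD difference per independent measure, nearly all sets were separated. The full LRM is therefore likely to fail either way.

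**Other readings of the two tests.** If they are measured again with assumed error (3-5 V SD, 5-10% of monofilament results flipped), specificity against the label falls to about 0.94-0.98 for biothesiometry and 0.90-0.95 for monofilament, and separation is no longer certain. The estimate is still inflated, because the repeat reading is correlated with the one that set the label.

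**NCS as the reference.** Patients are sampled 40 label-positive to 20 label-negative. Assume that the either-positive rule truly has 80% sensitivity and 90% specificity against NCS, and that 20% of clinic patients have abnormal NCS. The label-positive share is 0.16 + 0.08 = 0.24. Of 40 label-positive patients, 40 × 0.16/0.24 = 26.7 have abnormal NCS; of 20 label-negative patients, 20 × 0.04/0.76 = 1.05 do. Apparent sensitivity is 26.7/27.7 = 96%, and apparent specificity is 18.95/(18.95 + 13.33) = 59%. At 50% abnormal NCS the pair is 91% and 79%. NCS removes the circularity but not the selection.

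**The case against.** The strongest objection is that the plan never says the groups are the reference. NCS is the only test it calls a gold standard, and VI.A sizes the study on a nerve-conduction amplitude. Against NCS, or for painful versus non-painful DPN, none of the fixed results follows. This stands as a limit: the point is conditional. It does not remove the point. NCS is described as a standard for large fibres only, IV.D ties it to usual care for patients with neuropathy, and the groups are the only DPN classification that the plan defines.

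Second, the analysed values may not be the grouping readings. IV.D allows a later session, four spots and an NDS. This also stands: exactly 100% and certain separation hold only for the grouping readings at the defining cut-offs. Other versions remain biased by incorporation.

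Third, a reader might infer that these two tests are what breaks the full LRM. The documents do not support that, since about 29 or more other factors for 60 participants would probably separate the groups without them. A reader might also infer that the whole main endpoint is circular. It is not: PTT, MRI, CCM, AF, QST, Vagus, pinprick and NCS play no part in criterion 4, and the correlations and factor analysis do not use the label.

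**Conclusion.** The concern holds in a conditional form. It assumes that the reference and LRM outcome are group-defined DPN, that group 3 meets neither part of criterion 4, and that the grouping readings are analysed at the defining cut-offs. Then three results are known before any data are collected: 100% group 3 specificity for each defining test, 100% sensitivity in groups 1-2 for the either-positive rule, and complete separation of any DPN yes/no LRM with both readings. With repeat readings, a four-spot count or an NDS the figures are not fixed, but they are still biased.

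The harm specific to this problem lies in the accuracy table and in the univariate and reduced LRMs. There the comparison on group 3 specificity is tilted against the newer tests, and a reduced model can report perfect apparent accuracy from the label's own components. It should be fixed, but it does not undermine the study: it affects two comparators, and the accuracy of the other tests is not circular.

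**What to change.** - In IV.A and VI.B, name the reference for sensitivity and specificity and the outcome of each LRM.
- Wherever that is group-defined DPN, state in IV.B that group 3 meets neither part of criterion 4. Leave biothesiometry, monofilament and any NDS containing them out of every LRM with that outcome, including the factor reduction. Do not present their sensitivity, specificity or odds ratios as accuracy estimates, or show them only labelled as definitional.
- Relate the newer tests to these two through the planned correlations and factor analysis.
- Do not count group 4 in the specificity of any test used to select it.
- Add to VIII that accuracy against this label cannot by itself show early detection.
- If NCS is used as a second reference, remove it from the predictors, report how many in each group have it, and note that participants were selected on the two clinical tests.

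The cost is wording and fewer LRM factors, with no new patients or tests. The downside is that the study gives no unbiased accuracy estimate for the two clinical tests, which this design cannot give in any case; the comparison with clinical practice becomes one of association. NCS may be incomplete in groups 3-4. The excess of factors over participants in the full LRM is a separate problem that this change does not solve.
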